After the training session, trainees fill out an anonymous feedback form. The feedback questions will be structured according to Kirkpatrick's four levels of evaluation: reaction, learning, behavior, and results.³⁰ A draft of the feedback form questions is presented in Table 2.

Table 2. Training feedback form questions.

Item	Response options
1. [Reaction] What is your overall reaction to the course? It was:	(a) very good (b) good (c) average (d) poor (e) very poor
2. [Learning] Did you learn anything new?	(a) yes (b) no
If A – then: Please describe the most valuable thing you learned:	[free text]
If B – then: Please tell us anything you think we should be covering in future sessions to improve the usage of data in hospitals: [free text]	[free text]
3. [Behavior] Do you intend to use any of the training over the next three months?	(a) yes (b) no
If A – then: Wonderful, please tell us one way you intend to use the training over the next three months.	[free text]
If B – then: We are sorry to hear that. Could you briefly explain why you do not intend to use the training? Your feedback will help us improve the session for future attendees.	[free text]
4. [Results] Do you think that adopting a SPC approach to data management can improve your organisations quality and safety measures?	(a) yes (b) no
5. Any other comments about today?	[free text]

Study of the intervention

Design

The current study is a quantitative evaluation of the effect of the Making Data Count training intervention on SPC charts indicated in hospital board papers, comparing those hospitals which are randomly allocated to either an intervention group or a waitlist control group. An analysis of the feedback forms will also be conducted to improve future renditions of the training.

Sample size calculation

We plan to include 20 hospitals, of which 10 will be randomly allocated to the intervention group and 10 to the waitlist control group. The sample size is based on pragmatic

reasons, as it needs to accommodate the number of hospitals that the Making Data Count team can schedule and train in a year. Delaying training longer than a year was deemed unreasonable by the Making Data Count team for hospitals planning to take up the training.

[figure not shown]

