Based on our sample size calculation, a minimum of 16 hospitals with pre- and post-intervention measures is required to detect a 30-percentage point increase in the proportion of indicated SPC charts from 10% to 40% between control and intervention measures. The sample size was calculated with an alpha of 0.05 and a power of 0.80. Due to the study design (measurements taken of the outcome in a baseline period), adjustment for the correlation between pre- and post-intervention measures were made, estimated at $r=0.90$.³¹ The primary analysis will be conducted based on intention-to-treat. While only 16 hospitals are required, we have planned to include 20 on an ‘insurance principle’ in case some hospitals drop out.

Selection and randomization of hospitals

At the present time, SPC training cannot be mandated. The hospitals that take part will ultimately depend on their willingness and availability to experience training. The five-step selection and randomization process for hospitals is presented in Figure 3. **Step 1** involves obtaining contact information for all the hospitals identified as relying on R-A-G charts or two-point comparisons to present quality and safety performance metrics in their board papers (75 at the time the protocol is being written). **Step 2** involves the Making Data Count team inviting the hospitals to take up training over a specified 12-month period. As part of their informed consent, hospitals will be made aware that they may be offered training over either the initial 6-months or the later 6-months in a randomized fashion. **Step 3** involves selecting the 20 hospitals that first express an interest in taking up the training or a smaller number which do so after 30 days have passed (note that recruitment will continue until 20 express an interest – see Step 5). The Making Data Count team will email the list of

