the board papers (the denominator), for pre-intervention and post-intervention periods. To determine the absolute effect of the intervention we will compare the proportions of charts presented as SPC charts (between intervention and control arms) for each hospital and adjust for the proportion of SPC charts in the pre-intervention period. These differences will be compared between waitlist and intervention hospitals using a t-test and reported with 95% confidence intervals (a log transformation will be used if appropriate). To determine the relative effect (risk ratio) of the intervention, we will fit a zero-inflated negative Binomial regression model (outcome data are likely to be over-dispersed with a high number of zero counts), with the outcome of the number of SPC in the post-intervention period, fixed categorical effects for the intervention and the proportion of charts which were SPC charts in the pre-intervention period, and an exposure of the number of charts (in the post-intervention period). The offset here acts much like a denominator representing the number of opportunities each chart could have been depicted in an SPC format.

A sensitivity analysis based on the per-protocol group allocations will be performed if necessary. The remaining outcomes will be reported using descriptive statistics, e.g., counts, percentages, medians, and interquartile ranges. We will describe the proportion of control charts displayed as icons versus the full control chart.

Analysis of data from feedback forms.

Likert scale responses to each question on the feedback form will be described using medians and interquartile ranges. For the free-text responses, the number of positive, negative, and neutral comments will be reported. In addition, the available free-text responses will be thematically analyzed according to Braun and Clarke's method to reveal ways to improve future training or reasons others may (or may not) want to take it up.³⁴

Ethical considerations

This research has received ethical approval to conduct from the University of Warwick Biomedical and Scientific Research Ethics committee (BSREC 100/20-21). The research team declares no conflicts of interest to disclose. The research team will work closely with NHS Improvement's Making Data Count team to design and conduct the study, and their support will be acknowledged in the final manuscript. NHS Improvement will have no role in the analysis, interpretation of data, or in writing the manuscript.

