DISCUSSION

Summary

The summary will highlight whether the Making Data Count training intervention significantly increased control charts usage. Then it will compare the present results with those found in the previous, non-randomized evaluation.³⁵ We will explore how the responses to the feedback forms help us understand the effectiveness of the training. The literature will be reviewed for more recent publications nearer to the time this manuscript is written. Implications for clinical practice across types of care (e.g., health and social care) will be considered, along with the potential for the intervention's effectiveness to generalize to organizations outside England.

Limitations

Limitations are acknowledged within this protocol having to do with methods and the potential for our results to generalize. Regarding study methods, we are unable to blind the first set of reviewers to whether a hospital belongs to the intervention or control group. This is not possible because they will be looking directly at the board papers as they extract the initial information, and the board papers will inevitably contain identifiable information. The second set of reviewers will be blinded, as they will only be looking at extracted charts. Second, while board papers provide an objective measure of whether control charts are used, they are silent on how control charts are used. While the existence of control charts is a

necessary pre-condition for their being used well, it is possible that they are not being used as part of a broader quality improvement methodology that could positively impact patient care.

In that sense, our study only seeks to establish whether the necessary conditions for SPC-based improvement have been met. A future study may investigate how SPCs are used.

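### The zero-inflated negative binomial model for the risk ratio is too large for 20 hospital counts: with ordinary large-sample inference its 5% test would reject about 10-28% of the time under no effect

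*Combined protocol and SAP*

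**What the plan says.** The number of hospitals is given under the sample size heading: "We plan to include 20 hospitals, of which 10 will be randomly allocated to the intervention group and 10 to the waitlist control group". That section also states that "a minimum of 16 hospitals with pre- and post-intervention measures is required".

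Selection of board papers from hospitals: two papers are retrieved per hospital, one before and one after, giving 40 papers. Only one post-intervention count per hospital enters the model.

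Planned Analyses, Analysis of data from board papers: the absolute effect is a baseline-adjusted comparison of proportions by t-test with 95% confidence intervals. For the risk ratio, "we will fit a zero-inflated negative Binomial regression model (outcome data are likely to be over-dispersed with a high number of zero counts". The outcome is the post-period number of SPC charts. The covariates are arm and baseline SPC proportion, worded as categorical effects, and the exposure is the post-period number of charts. This part of the protocol does not specify the inflation part, cut-points for the baseline categories, the inference method, a small-sample correction or a rule for non-convergence.

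Abstract, Methods: the primary analysis is the baseline-adjusted difference between arms, with 95% confidence intervals. Discussion, Summary: "The summary will highlight whether the Making Data Count training intervention significantly increased control charts usage".

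**The concern.** The model needs an intercept, an arm effect, a baseline effect (more than one if baseline has over two categories), a dispersion parameter and at least one inflation parameter. That is 20/5 = 4 hospitals per parameter, or 16/5 = 3.2 at the minimum size. Large-sample standard errors are not trustworthy there. Excess zeros and over-dispersion explain much the same feature of the data, so the fit can barely separate them and tends to understate the uncertainty of the arm effect.

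The likelihood also has the wrong form, which is a secondary point. The outcome is a count out of a known total, but a negative binomial has no upper bound.

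At stake is a published risk ratio with an interval that is too narrow and, if a p-value is attached, a false-positive rate well above 5%.

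**Working it through.** **Inputs from the protocol.** 10 + 10 hospitals; 16 at minimum; 10% versus 40% SPC use; "The sample size was calculated with an alpha of 0.05 and a power of 0.80"; pre-post correlation 0.90; one post count per hospital; many zeros and over-dispersion expected.

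**Inputs assumed.** Charts per paper, zero share, dispersion, two-sided alpha and the form of the inflation part. The protocol gives none of these, so ranges are shown.

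**Step 1: the stated sample size.** For 10% versus 40%, with mean 0.25:

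n = [1.96√(2 × 0.25 × 0.75) + 0.842√(0.09 + 0.24)]² / 0.30² = 31.5, or 32 per arm.

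With continuity correction this becomes 37.9, or 38 per arm. Multiplying by 1 − 0.90² = 0.19 gives 38 × 0.19 = 7.22, so 8 per arm and 16 in total. The figure of 16 reproduces. It is for a difference in proportions and does not cover the count model.

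**Step 2: false-positive rate of the planned model.** No training effect; 1,000 simulated trials per setting. The model was fitted by maximum likelihood with log(charts) as offset, baseline as a median split or continuous, and inflation constant or (for the Wald tests) depending on arm. Ranges run over these versions. Percent rejecting at nominal 5%:

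| Setting (10% mean use and 20 hospitals unless stated) | Zeros | Wald z | Wald, t reference | Likelihood ratio | Baseline-adjusted linear model |
|---|---|---|---|---|---|
| 60 charts | 40% | 12.8-14.8 | 10.6-12.7 | 10.9-12.4 | 4.6 |
| 30 charts | 50-51% | 13.0-18.9 | 10.4-15.7 | 12.0-15.5 | 4.3-4.8 |
| 30 charts, more zeros | 64% | 17.2-25.8 | 14.2-20.4 | 14.9-23.7 | 2.9 |
| Data from the planned model | 45-50% | 13.0-18.0 | 10.1-15.0 | 12.2-14.1 | 4.1-4.2 |
| Data from the planned model, more zeros | 64% | 22.4-26.0 | 18.2-21.1 | 20.8-21.4 | 4.8 |
| Few zeros, low dispersion | 23% | 9.4-10.4 | 6.7-7.2 | 8.2-8.5 | 5.3 |
| 25% mean use | 34% | 9.7-10.2 | 7.2-8.4 | 7.8-8.4 | 5.2 |
| 16 hospitals | 45% | 15.9-17.4 | 11.1-12.8 | 13.6-14.7 | 3.9 |
| 200 hospitals (check) | 45% | 5.0-5.7 | 4.8-5.4 | 4.6-5.0 | 4.5 |

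Monte Carlo error is about ±2 to 3 points for the inflated rates; for example, 1.96√(0.15 × 0.85/1000) = 0.022. The return to 5% with 200 hospitals shows that the cause is the number of hospitals and not the code.

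In the 20-hospital settings with 10% use and 40-64% zeros, a dispersion or inflation parameter ran to its boundary in about 20-78% of fits. No standard error could be computed in up to about 4%.

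**Step 3: separate simulations.** With 8-44 charts per paper and 30%, 60% or 75% of hospitals with no baseline SPC use, Wald z rejected 13.8%, 19.2% and 28.2%. A further simulation with 30-65% non-users gave 12-19%, whether baseline was continuous or categorical. Over all simulations, t-based analyses of the absolute difference rejected about 2-7%.

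**Step 4: meaning for the interval.** A Wald test that rejects 10-28% under no effect corresponds to a 95% interval that contains the true ratio of 1 in only 100 − 28 = 72% to 100 − 10 = 90% of trials.

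**Step 5: form of the likelihood.** With mean 0.4 × charts and dispersion 0.5-1.5, a negative binomial puts about 4-10% of its probability on more SPC charts than there are charts.

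**The case against.** The strongest reply is that the headline does not rest on this model. A reader might infer from the Planned Analyses, which place both estimates under the main analysis, and from the Summary, which does not say which result decides, that a spurious ratio could carry the claim of a significant increase. If either result counted, the simulated error would be 16-28%. The documents do not state that rule. The abstract names the baseline-adjusted difference as primary, and the sample size is set in percentage points. This reply stands and limits the severity. What remains is that the hierarchy is not repeated where the results will be analysed and summarised.

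The second reply is that the size of the inflation is not a property of the protocol. It depends on assumed chart counts, zero share and dispersion, and on Wald inference that the protocol does not name. The protocol also attaches 95% intervals expressly to the t-test only; an interval for the ratio is implied. This stands as a limit on precision. It does not remove the problem: the mildest settings still gave 9-10% with Wald z, and in the frequent-zero settings the alternative tests still gave 10% or more.

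The third reply is that any log-link ratio fails when an arm has no SPC charts. This is foreseeable, because recruitment starts from 75 hospitals whose papers lacked them. With 75% of hospitals at zero at baseline, an arm was empty in about 9% of trials in one simulation and 5-16% in another; with 90% at zero, 28-62%. This stands, and the replacement needs a rule for it.

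**Conclusion.** The concern holds for the relative effect only. With 20 hospitals and ordinary Wald inference, the planned model's nominal 5% test would reject about 10-28% of the time when training does nothing, and about 12% or more when zeros are frequent, as the protocol anticipates. Its 95% interval would be too narrow to match. The range rests on the assumptions listed in the working and should be reported with them. The primary absolute comparison is not affected, and the sample size of 16 is not in error on this point. Severity: should-fix.

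**What to change.** In the Planned Analyses:

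- Replace the zero-inflated model with a log-link quasi-Poisson regression of each hospital's post-period SPC proportion on arm and continuous baseline proportion. Use leverage-corrected HC3 standard errors and a t distribution with hospitals minus 3 degrees of freedom (20 − 3 = 17). The leverage correction matters: uncorrected sandwich errors rejected 10-21%. The corrected version rejected 3.5-5.0% under no effect. It covered the true ratio 95.9% of the time at a ratio of 3.1 and 96.7% at 2.25.
- State that hospitals are weighted equally, so the ratio compares mean hospital proportions and not pooled charts. This differs from the planned chart-count exposure and changes what the ratio estimates.
- State that if an arm has no SPC charts, or the model cannot be fitted, only the absolute difference is reported.

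In the Planned Analyses and the Summary, repeat the abstract's hierarchy: the baseline-adjusted absolute difference alone decides whether use significantly increased, and the ratio is supportive.

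The cost is analysis wording only. The downside is a wider interval for the risk ratio and, occasionally, no ratio reported.

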selected hospitals to the research team. **Step 4** involves the research team randomizing the available hospitals to either the intervention group or waitlist control group. Randomization will be stratified based on the number of overnight beds from the most recently available count available from NHS England (dichotomized at the medium, to create “large” and “small” hospitals).³² **Step 5** involves the research team emailing the randomized lists back to the Making Data Count team to commence scheduling. If the original list contains fewer than 20 hospitals, then the Making Data Count team will continue recruitment and another list of hospitals will be sent to the research team to randomize in the same stratified manner each month. The purpose of this is pragmatic – to ensure trainings can commence in a timely fashion, alongside the research being conducted.

Figure 3. Five steps in the selection and randomization process

Scheduling training

Hospitals allocated to the intervention group will be invited to schedule training over an initial five-month period. Hospitals allocated to the waitlist control group will be invited to schedule a training over a later five-month period. A hypothetical training schedule appears

in Figure 4. Approximately two hospitals may receive training each month, but the schedule will ultimately depend on hospital availability and training capacity.

[figure not shown]
Figure 4. Example of potential schedule

Scheduled Training Order	Group 1 - Intervention
Month 1	Hospital A
Month 1	Hospital G
Month 2	Hospital D
Month 2	Hospital F
Month 3	Hospital C
Month 3	Hospital I
...	...
Group 2 – Waitlist	
Month 6	Hospital K
Month 6	Hospital L
Month 7	Hospital J
Month 7	Hospital B
Month 8	Hospital H
Month 8	Hospital E
...	...

Selection of board papers from hospitals

From each hospital, two board papers will be retrieved for a total sample of 40 papers. For the hospitals in the intervention group, we will retrieve the papers published in the nearest month before the intervention was delivered (pre-intervention observation) and approximately five months after the intervention was delivered (post-intervention observation). This selection process is represented in the top half of Figure 5. As boards do not publish their papers every month, it is not always possible to sample precisely one month pre-intervention or five months post-intervention.

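### The risk-ratio model enters the baseline SPC proportion as an unbanded categorical effect; read literally, about 2 to 14 of the 20 hospitals would add nothing to the arm contrast

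*Combined protocol and SAP*

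**What the plan says.** The relative effect is described under Planned Analyses, Analysis of data from board papers: "we will fit a zero-inflated negative Binomial regression model". The reason given is that "outcome data are likely to be over-dispersed with a high number of zero counts". The outcome is the post-intervention count of SPC charts, with the post-intervention number of charts as exposure. The covariates are "fixed categorical effects for the intervention and the proportion of charts which were SPC charts in the pre-intervention period". No bands or cut-points are given for the baseline proportion, and no continuous form is mentioned.

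The data set is small. Under Sample size calculation: "We plan to include 20 hospitals, of which 10 will be randomly allocated to the intervention group", with the other 10 on the waiting list. Under Selection of board papers from hospitals: "From each hospital, two board papers will be retrieved for a total sample of 40 papers". That is one pre and one post paper per hospital, so the model has 20 rows.

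The absolute effect is analysed separately, by a t-test adjusted for baseline.

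**The concern.** The baseline proportion is SPC charts divided by all quality and safety charts in one paper, and the denominator differs between hospitals. Apart from hospitals at exactly 0%, two hospitals will rarely share a value. Under unbanded categorical coding, each non-zero hospital then tends to get its own parameter. That parameter fits the hospital's own count, so the hospital says nothing about training in the count part. If its post-intervention count is zero, the coefficient also runs off to minus infinity.

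The estimated risk ratio would then rest mainly on hospitals with a baseline of exactly zero. If the model failed to fit, the analyst would have to choose bands after seeing the data, in one of the two estimates described under the main analysis.

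**Working it through.** **1. The plan's own figure.** "The sample size was calculated with an alpha of 0.05 and a power of 0.80", for 10% versus 40% and a pre-post correlation of 0.90. Taking a two-sided test (sidedness is not stated):

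- n per arm = [1.96·√(2·0.25·0.75) + 0.84·√(0.10·0.90 + 0.40·0.60)]² / 0.30², which rounds up to 32, or 38 with continuity correction.
- Baseline adjustment factor: 1 − 0.90² = 0.19.
- 38 × 0.19 = 7.22, so 8 per arm and 16 in total.

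The stated minimum of 16 reproduces. It does not use the risk-ratio model, so this point leaves it unchanged.

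**2. Parameter count.** Let k hospitals have distinct non-zero baselines and the other 20 − k have zero. There are k + 1 levels. Adding the arm, the dispersion and one zero-inflation intercept (assumed, since the plan does not specify that part) gives k + 4 parameters. A level with a waitlist and b intervention hospitals carries arm information ab/(a + b). All 20 hospitals in one balanced level would give 10·10/20 = 5. If the zero-baseline hospitals split evenly, the share kept is (20 − k)/20.

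| k | Levels | Parameters | Hospitals left in contrast | Information kept |
|---|---|---|---|---|
| 2 | 3 | 6 | 18 | 0.90 |
| 5 | 6 | 9 | 15 | 0.75 |
| 10 | 11 | 14 | 10 | 0.50 |
| 15 | 16 | 19 | 5 | 0.25 at most |

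**3. How large k could be.** The documents do not say, so it was simulated (2,000 runs per scenario, 20 hospitals, 10 per arm). The assumptions are 10–30, 20–60 or 40–100 charts per paper; a stated share of hospitals with a true baseline of zero; and beta-binomial spread of 0.2 among the rest. The plan's 10% planning rate serves as the overall mean baseline, except in the last row, where it is 3%. Ranges run over the three chart-count assumptions.

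| True zeros | Mean baseline | Non-zero hospitals | Hospitals in levels with both arms | Hospitals lost | Parameters | Information kept |
|---|---|---|---|---|---|---|
| 0% | 10% | 10.6–14.1 | 5.9–10.0 | 10.0–14.1 | 14.0–17.9 | 0.26–0.47 |
| 25% | 10% | 9.6–12.1 | 8.0–10.9 | 9.1–12.0 | 13.1–16.0 | 0.37–0.52 |
| 50% | 10% | 7.9–9.1 | 11.0–12.4 | 7.6–9.0 | 11.6–13.0 | 0.52–0.60 |
| 75% | 10% | 4.8–5.0 | 15.1–15.3 | 4.7–4.9 | 8.7–8.9 | 0.74–0.75 |
| 90% | 3% | 1.8–2.0 | 18.0–18.2 | 1.8–2.0 | 5.8–6.0 | 0.90 |

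Every scenario gave 0.94 to 1.00 levels per non-zero hospital. With 16 hospitals the pattern is the same.

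**4. Effect on precision.** With equal information per hospital, the standard error of the arm effect grows by 1/√(information kept): 1/√0.90 = 1.05, 1/√0.75 = 1.15, 1/√0.26 = 1.96. Simplified negative binomial fits (dispersion fixed at 0.5, no zero-inflation part, 20–60 charts, mean baseline 10%) put the ratio of the categorical to the continuous standard error at about 1.4 with 75% true zeros, 1.7 with 50%, and 1.9 with 25% or none. These ratios depend on the assumed post-intervention counts and indicate order of magnitude only.

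**5. With a linear baseline term.** The count part has 3 parameters (intercept, arm, baseline), or 5 with dispersion and one inflation intercept. All 20 hospitals stay in the contrast.

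**The case against.** The strongest reply is that the sentence is loosely worded. The word 'categorical' may have been meant for the intervention only, or bands may have been intended and left out. Elsewhere the baseline is treated as a number: the t-test adjusts for the proportion, and the sample size uses a pre-post correlation. This is fair as to intent, but the text states neither alternative. If bands were meant, the cut-points are missing; if a continuous term was meant, the sentence is wrong. A correction is needed on every reading.

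The second reply is that the loss may be small. Problem description says the 75 hospitals in the recruitment pool had papers without SPC charts, so nearly all baselines could be zero and only about 2 of 20 hospitals would be lost. This stands as the lower end of the range. It is not the only supportable case. The same passage calls those papers predominantly, rather than wholly, made up of other formats. The review dates from 2020, while baseline papers come from just before training. The plan itself works with 10%.

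Third, categorical coding is not wrong in itself. A single split into zero and non-zero also uses one degree of freedom. This stands, and the fix allows for it.

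**Conclusion.** The point holds for the model as written. Unbanded categorical coding makes almost every non-zero hospital its own level and takes it out of the arm contrast in the count part. The size is uncertain: about 5 to 14 of 20 hospitals at a mean baseline of 10%, and about 2 of 20 with 90% true zeros and a mean of 3%. Chart counts, baseline spread and shares of zeros are assumptions, since the documents give none of them.

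A reader might infer three stronger things that the documents do not support:

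- **That many hospitals will certainly be lost.** This depends on the number of non-zero baselines, which is not stated.
- **That the model is close to saturated in general.** It is so only when most baselines are non-zero: 19 parameters for 20 counts at k = 15, but 9 at k = 5.
- **That the trial's primary comparison or power is undermined.** The Abstract defines the primary analysis as the baseline-adjusted difference in use, and the sample size targets a percentage-point difference. Neither uses this model. The risk ratio alone is at stake.

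**What to change.** In the risk-ratio sentence under Planned Analyses, replace the covariate description with: 'a fixed categorical effect for the intervention and a continuous (linear) term for the pre-intervention SPC proportion'. If a categorical form is preferred, name one split in advance, such as zero versus non-zero. Settle this before the post-intervention papers are coded, so that the data do not drive the choice.

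The cost is one sentence, one degree of freedom for the baseline term, and no new data. The linear term has a small downside: it assumes a log-linear relation between baseline proportion and post-intervention rate, which 20 hospitals can barely test. The split avoids that assumption but discards differences among the non-zero baselines.
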